For group analysis, the 3-D anatomical datasets of each subject will be spatially normalized and converted to the standard anatomical space. The resulting normalization parameters will be applied to the 4-D time series datasets. To estimate the main effect of a task per group, the group analysis will be carried out using a three-way analysis of variance (ANOVA) with subject as a random factor and the task and group as fixed factors ($p \leq 0.025$, voxelwise corrected) to identify (1) shared abnormalities in all patients vs. controls, and (2) distinct abnormalities between SD vs. SD/VT patients. Statistical differences in brain activation extent will be assessed using the subtraction method within the three-way ANOVA design. This univariate data analysis will provide information about the extent and intensity of brain activation in different groups (i.e., SD and SD/VT patients vs. controls and SD patients vs. SD/VT patients).

To further our knowledge of functional brain abnormalities in SD and VT, we will perform multi-stage brain network analysis, which will allow for identification of abnormal brain networks and the relationship between the key network regions, possibly contributing to the pathophysiology of these disorders. For this, we will first perform a correlation analysis between functional and structural datasets in SD and SD/VT patients to determine the brain regions of abnormal function with underlying structural changes. The structural data will be derived from the *Studies 1.3.2 and 1.3.3*.

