To date, oral medications are known to provide little relief from SD and VT symptoms, and, thus, these patients are not systematically prescribed any medications (Adler, 2000). However, some patients report anecdotal benefits from taking lorazepam, clonazepam, diazepam, gabapentin, as well as some receive anti-depressants and anti-anxiety drugs to cope with their disorder-associated depression and anxiety. Recently, a series of clinical trials have reported significant beneficial effects of sodium oxybate on symptom improvement in treatment-refractory hyperkinetic movement disorders, including dystonia and ET ([name] et al., 2005a; [name] et al., 2005b; Arpesella et al., 2009). This medication seems to target more efficiently the tremor symptoms. Hence, it is possible that it may represent an alternative treatment option for SD/VT patients, whose symptoms are not fully responsive to botulinum toxin treatment.

However, despite remarkable improvement of symptoms in patients with movement disorders, the central effects of sodium oxybate also remain unknown. The absence of such information is a significant problem because it prevents the development of a scientific rationale for the use of a potentially beneficial novel pharmaceutical agent for the treatment of SD and VT. The objective of this aim is, therefore, to identify the mechanisms of central action of a promising novel medication, sodium oxybate, in SD and SD/VT patients as well as to determine the extent of central effects of a combined use of sodium oxybate and botulinum toxin treatments. Our working hypothesis is that the greater beneficial effects of sodium oxybate treatment in SD/VT patients compared to SD patients are due to a greater extent of modulation of their abnormal brain activation. This hypothesis has been formulated based on our preliminary data and will be tested using the experimental approach of fMRI during symptomatic speech production before and after treatment in SD and SD/VT patients, who report improvement of their symptoms after alcohol intake. The rationale for these studies is that the explanation of central mechanisms of action of sodium oxybate in SD and VT patients would help establish a scientific rationale for this drug as a new treatment option for patients who have failed other therapies.

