II. Sodium oxybate modulates abnormally increased activation in SD and SD/VT patients. Using a sparse-sampling BOLD fMRI design and symptomatic speech production, we examine the effects of sodium oxybate on brain activation abnormalities in 3 SD and SD/VT patients to evaluate the mechanisms of central action of this novel pharmacological agent. Compared to healthy controls, before treatment, all patients exhibited typically increased brain activation during symptomatic speech production ($p \leq 0.05$, corrected) (Fig. 3-I) similar to abnormalities described before (Haslinger et al., 2005; Ali et al., 2006; [name] and Ludlow, 2010) and in our 1.2.2 *Preliminary Studies* above. After treatment, patients' brain activation was significantly attenuated and followed a nearly normal pattern present during normal speech production, with only few regions remaining hyperactive ($p \leq 0.05$, corrected) (Fig. 3-II). A two-tailed paired *t*-test calculation using the measure of the total number of significantly active brain voxels before and after treatment in patients showed that the drug-induced attenuation of abnormal functional activation was in average 49% ($p = 0.017$) (Fig. 3-III). Specifically, sodium oxybate treatment significantly decreased and normalized abnormally elevated brain activity in the prefrontal, premotor and auditory cortices as well as in the basal ganglia, thalamus, and cerebellum. In 1.2.2 *Preliminary Studies* presented above, we found these regions to have a greater extent of abnormal activation in SD/VT patients compared to SD patients.

[figure not shown]

Figure 3 depicts differences in brain activation in SD and SD/VT compared to healthy controls before (I) and after (II) treatment with sodium oxybate (voxelwise $p \leq 0.05$, corrected). Panel (III) shows significantly decreased number of hyperactive brain voxels after the treatment compared to the before treatment baseline in patients ($p = 0.017$).

Collectively, our preliminary data indicate that sodium oxybate is effective in SD patients and especially in those who present with a VT component. Furthermore, our data suggest that the effects of sodium oxybate treatment are exerted through the modulation of overly increased brain activation.

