Following the initial (baseline) fMRI session, patients will receive an individualized tolerable and efficacious single dose of sodium oxybate, given orally in the office. Patients' symptoms will be evaluated and videotaped one hour after receiving this dose with the immediately followed-up second fMRI session, during which the patients will be asked to produce the same tasks performed during the pre-treatment fMRI study. Patients' post-treatment scans will be compared to their pre-treatment scans to identify differences in brain activation abnormalities due to the effects of sodium oxybate treatment. Voice and speech production during both scanning sessions will be digitally recorded for acoustical analysis and correlations with the central effects of the treatment.

Data analysis. Using AFNI software, fMRI data analysis will include initial pre-processing followed by analysis of the task-related responses using multiple linear regression with a single regressor for each task convolved with a canonical hemodynamic response function, as described above in *1.3.1 Study of Specific Aim #1*. For group analysis, a two-way ANOVA will be conducted with subject as a random factor and task as fixed factor (corrected $p \leq 0.025$). Conjunction analysis at a cluster significance threshold of $p < 0.005$ will determine common and distinct regions of activation within the patient group during task production in the pre- and post-treatment fMRI sessions. Finally, pre- and post-treatment neuroimaging findings will be correlated with the behavioral data derived from acoustical analysis of voice and speech recordings.

Additionally, to determine the extent of sodium oxybate effects on speech network dynamics, we will re-examine functional and effective network connectivity using the same PPI and DCM procedures as described in the *Study 1.3.1*.

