Study population and Sample size. To our knowledge the central effects of sodium oxybate has not been reported. Therefore, to estimate the number of patients to be included in this study, we reviewed our pilot fMRI study in SD and SD/VT patients. Compared to baseline, we found an average of 49% reduction of overly increased brain activation after treatment with sodium oxybate. Power analysis determined a sample size of 22 patients in each group to have 80% power at 0.025 to detect changes in brain activation when comparing before and after treatment conditions. We propose to recruit 25 ethanol-responsive SD and SD/VT subjects per group to account for the subjects' dropout possibilities and to increase statistical power.

2.3.2 Study #2: Evaluation of combined central effects of sodium oxybate and botulinum toxin treatments in patients with SD and SD/VT using fMRI during symptomatic speech production. In this study, we will use the same fMRI design as used in the Similar to *Studies 1.3.1* and *2.3.1* to examine the combined effects of sodium oxybate and botulinum toxin on brain activation changes due to the treatment.

We estimate that about 40% of all recruited patients (mostly with ADSD) will report some benefits from botulinum toxin injections. These patients will be enrolled in this study and will undergo the third scanning session after receiving their botulinum toxin treatment. They will be asked to take their individualized dose of sodium oxybate T.I.D. after the completion of the *Study 2.3.1* and until the end of this study. We predict that about 60% of SD (typically ABSD) and SD/VT patients recruited to the *Study 2.3.1* will report limited, if any, benefits from botulinum toxin treatment. These patients will, therefore, be replaced with newly recruited patients, whose symptoms do response to both alcohol intake and botulinum toxin treatment. Thus, at the time of this study, all patients will be treated with both sodium oxybate and botulinum toxin injections. The decision of whether sodium oxybate should be continued after the completion of all studies in this proposal will be made by the patient and his/her referring physician.

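### Aim 2 hypothesises greater modulation in SD/VT than in SD, but names no contrast of the pre-to-post change between the groups and no scale for it; with unequal baselines the answer depends on the scale

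*Combined protocol and SAP*

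**What the plan says.** The hypothesis is comparative. Section 2.1, like the Specific Aims page, holds that the "greater beneficial effects of sodium oxybate treatment in SD/VT patients compared to SD patients are due to a greater extent of modulation" of abnormal activation.

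The analysis in 2.3.1 is not comparative. Patients' "post-treatment scans will be compared to their pre-treatment scans to identify differences in brain activation abnormalities". At group level, "a two-way ANOVA will be conducted with subject as a random factor and task as fixed factor". A conjunction analysis then looks for "common and distinct regions of activation within the patient group during task production in the pre- and post-treatment fMRI sessions". Correlations with the acoustic data and repeat connectivity analyses follow. The activation model has no diagnosis factor, no session factor and no baseline term. By contrast, 1.3.1 uses a "three-way analysis of variance (ANOVA) with subject as a random factor and the task and group as fixed factors". Study 2.3.2 adopts the 2.3.1 pipeline unchanged.

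On baselines, 1.2.2 reports abnormalities of greater spatial extension in SD/VT (7 patients per group). Section 2.2.2 says of the regions attenuated by the drug that "we found these regions to have a greater extent of abnormal activation in SD/VT patients compared to SD patients". The drug effect is given once, pooled over both diagnoses: "we found an average of 49% reduction of overly increased brain activation after treatment with sodium oxybate". Section 2.2.2 shows that this is a fall in the number of significantly active voxels.

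**The concern.** A claim that one group is modulated more needs a test of the difference between the two groups' changes, and a statement of what more means. The plan gives neither, although its own pilot suggests that the groups start from different points in the relevant regions. Separate before-and-after results in SD and SD/VT could then be compared informally, on whichever scale is to hand. The principal conclusion of Aim 2, that SD/VT patients benefit more because their brains are modulated more, could be reached when the drug acts proportionally alike in both groups. More extensive disease before treatment would then be reported as a disorder-specific drug mechanism. Adding a group-by-session term on the raw scale alone would not settle this.

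**Working it through.** **The plan's own figure.** Section 2.3.1 gives 22 per group for 80% power at 0.025 to detect a before-versus-after change. It gives no SD of the change, so 22 can be neither confirmed nor refuted. A paired two-sided test reaches 80% power with 22 if the mean change is 0.70 of its SD. Either way, the figure concerns change over time, not a difference in change between diagnoses.

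**The scale problem on the pilot's measure** (baseline counts assumed: SD 1000 voxels, SD/VT 1500).
- Same 49% fall: 0.49 × 1000 = 490 and 0.49 × 1500 = 735 voxels lost. Raw change favours SD/VT; percentage change is equal.
- Same fall of 490 voxels: 490/1000 = 49% and 490/1500 = 32.7%. Raw change is equal; percentage change favours SD.

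**How often raw change would mislead.** Inputs from 1.3.1: signal 0.63 (s.d. 0.16) in SD and 0.39 in controls, so the excess is 0.63 − 0.39 = 0.24. Assumed: s.d. 0.16 at each scan; pre-post correlation ρ of 0.5 or 0.8; SD/VT excess R times that of SD; the drug removes 49% of the excess in both groups. From 2.3.1: 25 per group. The test is a two-sample t-test on change at two-sided 0.025. The true difference in raw change is 0.49 × 0.24 × (R − 1). The SD of change is 0.16 × √(2(1 − ρ)), that is 0.160 or 0.101. Results over 3,000 simulated trials per case:

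| R | Difference in raw change | Declared different, ρ = 0.5 | ρ = 0.8 |
|---|---|---|---|
| 1.25 | 0.029 | 5.4% | 10.7% |
| 1.5 | 0.059 | 17.0% | 40.3% |
| 2 | 0.118 | 62.2% | 96.2% |

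The nominal rate is 2.5%, counting both directions. An exact noncentral-t calculation agrees to within a percentage point. If the drug instead removes the same absolute amount in both groups, the raw-change test stays at 2.3% to 2.5% for every R.

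**How often percentage change would mislead.** Assume the same absolute fall in both groups (0.118 = 0.49 × 0.24, or 0.309 = 0.49 × 0.63), total SD/VT baseline signal 25% or 50% higher, and ρ of 0.5 to 0.8. Percentage change then falsely favours SD in 4% to 96% of trials (nominal 1.25% in that direction).

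**Whether a baseline covariate resolves it.** With the post-treatment value regressed on group and the pre-treatment value, under the assumptions of the table (R = 1.25, 1.5, 2):
- Identical 49% effect: 2.0%, 2.6%, 2.6% at ρ = 0.5, but 5.1%, 14.3%, 39.9% at ρ = 0.8, toward SD/VT.
- Identical absolute effect: 6.5%, 19.5%, 54.0% at ρ = 0.5 and 4.0%, 7.7%, 19.7% at ρ = 0.8, toward SD.

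The covariate can therefore err in either direction.

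**The case against.** The strongest reply is that the plan contains no raw-change test between the groups, so error rates for such a test are not the plan's. That is right. A reader might infer that the hypothesis will be read from raw pre-to-post differences; 2.3.1 does not say so, and the only scale the documents use for the drug effect is a percentage. What stands is that the contrast and its scale are both open. The repeat connectivity analyses do not fill the gap: 1.3.1 includes SD-versus-SD/VT comparisons for them, but nothing states a comparison of pre-to-post change, and connectivity is not extent of activation.

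A second reply is that the Specific Aims page expects additional abnormalities in SD/VT that are modulated to a greater extent. On that reading, removing more abnormal activation is the hypothesis itself and no artefact. This is fair, and it is why the scale must be declared. An absolute difference is a legitimate result, but it does not by itself show that the drug acts differently in SD/VT.

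Third, a reader might infer that the pilot found more intense activation in SD/VT. It reports greater extent, gives no intensity figure, and also describes areas distinct to SD. On a voxel count greater extent is a higher baseline; on signal change it need not be.

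**Conclusion.** The concern holds in this form: Aim 2's comparative hypothesis has no specified between-group contrast of change and no specified scale, and the pilot gives reason to expect baselines unequal in extent. The direction of the answer can then depend on the scale. An identical proportional effect shows as greater raw change in SD/VT, and an identical absolute effect as smaller proportional change there.

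The size is not known. The illustrative 17% to 40% at a 1.5-fold excess rests on an assumed baseline ratio, pre-post correlation and spread, and on applying a voxel-count percentage to signal change. None of these rates is an estimate for this trial. Nor do the documents support the view that the relative scale is the correct one, or that adjusting for the pre-treatment value would remove the problem. The groups are diagnoses rather than randomised arms, and error in the baseline scan biases the adjusted comparison. The plan should be amended on this point, because it determines what Aim 2 may conclude.

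**What to change.** In 2.3.1 Data analysis, and by reference in 2.3.2:
- Prespecify the SD/VT-versus-SD contrast of the pre-to-post change (group by session).
- Estimate it on both the absolute scale and a baseline-relative scale (percentage change, as in the pilot, or log post/pre).
- Use regions that are active at baseline, so that the ratio is stable, but not selected from the same patients' baseline abnormality; for example, define them anatomically or from other participants. The Human Subjects section expects 12 of the 25 patients per group to reuse their Aim 1 scan as the Aim 2 baseline, so choosing regions because those scans were abnormal would build regression to the mean into the change.
- Claim greater drug modulation in SD/VT only if both scales support it. If only the absolute change is larger, report it as compatible with more abnormal activation before treatment.
- Keep any model with the pre-treatment value as a covariate to a sensitivity analysis at most.

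No new data are needed, since each patient already has a pre- and a post-treatment scan. The cost is one additional contrast and a stricter criterion, with some loss of power for the claim. For scale, 22 per group gives 80% power at two-sided 0.025 only for a between-group difference of about 0.96 SD of the change, so the contrast should be reported with its confidence interval.

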Our long-term goal is to determine the pathophysiology of SD and related disorders, such as VT, and develop new diagnostic and treatment options for these patients. The objective of this application is to identify brain abnormalities in SD and SD/VT patients as the basis for characterization of central mechanisms underlying symptom improvement following the use of sodium oxybate. Our central hypothesis is that, compared to SD patients, SD/VT patients will have additional brain abnormalities within the sensorimotor brain circuits controlling voice production, which are being modulated to a greater extent with sodium oxybate treatment. We further postulate that the clinical efficacy of sodium oxybate treatment will correlate with its central modulatory effects. The rationale for the proposed research is that identification of distinct brain mechanisms underlying SD and SD/VT clinical manifestations would provide the necessary insights into the pathophysiology of these disorders, while understanding the neural correlates of sodium oxybate action would allow establishment of a scientific rationale for the use of a novel treatment in these disorders.

We propose the following two specific aims:

1. Determine disorder-specific brain abnormalities in SD and SD/VT patients. Based on our preliminary data, our *working hypothesis* is that distinct brain abnormalities will be present in SD and SD/VT patients, who also share common abnormalities within the sensorimotor brain networks controlling voice production.

2. Characterize the central effects of sodium oxybate treatment in ethanol-responsive SD and SD/VT patients. Based on our preliminary data, our *working hypothesis* is that the greater beneficial effects of sodium oxybate treatment in SD/VT patients compared to SD patients are due to a greater extent of modulation of their abnormal brain activation.

At the completion of these studies, it is our expectation that we will have (i) identified characteristic profiles of brain abnormalities in SD and SD/VT patients, (ii) determined the extent of their modulation with a novel treatment, sodium oxybate, both of which will be critical for (iii) establishment of neural markers and a new therapeutic option for patients who do not benefit from botulinum toxin treatment alone. These results are expected to have an important positive impact, because they will fundamentally advance our knowledge of the pathophysiology of SD and VT as well as allow for improved treatment.

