Innovation. As noted above, the current lack of understanding of SD and VT pathophysiology renders us unable to develop better treatment options for these patients. On the other hand, uncertainties about the central mechanisms of action of both existing and novel therapeutic options further contribute to this challenge. We propose a series of multi-modal neuroimaging studies that will (1) identify functional and structural brain abnormalities in SD vs. SD/VT patients to characterize disorder-specific brain changes, which will provide a scientific framework for (2) elucidating the central mechanisms of action of a novel oral medication, sodium oxybate, as a treatment of SD and VT. Direct comparisons between SD and SD/VT patients and between the central effects of sodium oxybate and botulinum toxin treatments *in the same experimental setting* have clear benefits for successful identification of characteristic patterns of abnormal brain function that may be modulated by a targeted treatment. Furthermore, the proposed correlations between central effects of sodium oxybate and symptom improvement will enhance our assessment of this drug as a novel treatment option for SD and SD/VT patients, many of whom have failed available therapies.

The proposed research is innovative because it focuses not only on identification of distinct pathophysiological mechanisms underlying SD and VT but also because it holds the promise for characterizing the central effects of a novel oral medication, sodium oxybate, as a potential treatment for refractory symptoms in SD and SD/VT patients. The use of advanced multi-modal neuroimaging methodologies together with detailed and extensive analyses of brain functional and structural organization in SD and SD/VT patients is anticipated to yield potentially novel results, which will be critical for the establishment of criteria for improved clinical management of these disorders.

Approach

Specific Aim # 1: Determine disorder-specific brain abnormalities in SD and SD/VT patients.

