As the last step in network analysis, we will examine effective connectivity between the brain regions of interest (ROIs) showing abnormal PPI network(s) in order to identify direct and indirect influences between the regions within the network(s). For this, we will use dynamic causal modeling (DCM) in SPM8 software, which is a hypothesis-driven neurodynamics model that uses a bilinear state equation to characterize an experimentally perturbed cognitive system using a hemodynamic forward model (Friston et al., 2003). The 4-mm radius sphere ROIs will be used to extract time series from each individual's scanning sessions. DCM estimates 3 different sets of parameters: (1) input parameters that quantify how brain regions respond to external stimuli; (2) intrinsic parameters reflecting the effective connectivity that characterizes the coupling between regions, and (3) modulatory parameters that measure changes in effective connectivity induced by some experimental conditions. Based on the results of correlation analysis between functional and structural datasets, the model will be specified with a specific hypothesis of how the affected regions would likely interact with each other. Speech production will be used as a modulatory input to estimate the change in connection strength as a function of the speaking task relative to other conditions in patients with SD and SD/VT and controls. All parameters (intrinsic and modulatory) of the DCM model and their posterior probabilities will be assessed with Bayesian inversion by means of expectation-maximization algorithm. Within-group analyses will be conducted using both the local and global approaches. The local approach will estimate the significance of the parameters at the local connection level, whereas the global approach will use the Bayesian model selection to identify the set of modulatory connections that is most plausible in the context of speech production. While the local approach guarantees that the connections considered for the model selection are consistent across the subjects, the global approach finds the optimal combination of these consistent local. Statistical comparisons between groups (SD and SD/VT vs. controls; SD vs. SD/VT) will also be conducted at a corrected $p \leq 0.025$.

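### The Aim 2 activation model names neither session nor group, so the claim that SD/VT activation is modulated more than SD activation has no stated activation test, and the stated 80% power does not cover it

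*Combined protocol and SAP*

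**What the plan says.** **Hypotheses.** The Specific Aims page says SD/VT patients have additional abnormalities "which are being modulated to a greater extent with sodium oxybate treatment". For Aim 2 it postulates: "the greater beneficial effects of sodium oxybate treatment in SD/VT patients compared to SD patients are due to a greater extent of modulation". What is modulated is the abnormal activation. Section 2.1 repeats this and says it "will be tested using the experimental approach of fMRI during symptomatic speech production before and after treatment in SD and SD/VT patients".

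**Aim 2 activation analysis (2.3.1, Data analysis).** "For group analysis, a two-way ANOVA will be conducted with subject as a random factor and task as fixed factor". A conjunction step then describes common and distinct regions within the patient group across the two sessions. Imaging findings are correlated with voice measures. PPI and DCM are repeated using the Study 1.3.1 procedures. The design paragraph also says, in words, that each patient's post-treatment scans are compared with the pre-treatment scans.

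**Aim 1, for contrast (1.3.1).** A "three-way analysis of variance (ANOVA) with subject as a random factor and the task and group as fixed factors".

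**Power (2.3.1, Sample size).** 22 per group for 80% power at 0.025 to detect before/after change; 25 per group recruited.

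**Study 2.3.2.** Same pipeline, and power stated to be unchanged from 2.3.1. About 40% of patients are kept and about 60% are replaced by new recruits. The Protection of Human Subjects section instead gives all 25 per group (12 carried over from Aim 1 plus 13 new) a baseline scan and both post-treatment scans.

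**The concern.** A statement that one group changes more than another is tested by comparing the pre-to-post change between groups. The stated activation model has neither of the two factors needed. Someone following the plan as written could not test this part of the hypothesis. Someone filling the gap could choose the contrast after seeing the maps. The usual shortcut, significant in SD/VT but not in SD, does not test a difference between groups.

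The power statement adds to this. It can be read as covering Aim 2 as a whole, but it refers to the within-patient contrast alone. Carrying it unchanged into Study 2.3.2 also assumes that about as many patients contribute to each contrast there, and the documents leave that unsettled.

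**Working it through.** Below, SD means spasmodic dysphonia; standard deviation is written out.

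**1. Is the contrast stated anywhere?**
- Activation ANOVA (2.3.1): subject and task only. The cross-reference to Study 1.3.1 attaches to the task-response regression. The group model is then specified separately, without the group factor that Aim 1 names.
- Pre/post comparison in words: within patient, no group.
- Conjunction: describes overlap within the patient group; it does not test a difference in change.
- PPI and DCM carried over from 1.3.1: these include between-group comparisons (for DCM, "Statistical comparisons between groups (SD and SD/VT vs. controls; SD vs. SD/VT) will also be conducted"), but they concern connectivity, and no change-by-group contrast is written.
- Innovation section: "Direct comparisons between SD and SD/VT patients and between the central effects of sodium oxybate and botulinum toxin treatments" are promised, without a model.

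**2. Can the stated 22 be reproduced?** No, because no standard deviation of change is given. Section 2.2.2 says the "drug-induced attenuation of abnormal functional activation was in average 49" percent, with a two-tailed paired p = 0.017. The number scanned is ambiguous (three in all, or three per group). Backing out the paired effect, d_z = t/√n:
- n = 3: t = 7.57, d_z = 4.37, requiring 4 patients (two-sided 0.025, 80% power).
- n = 6: t = 3.52, d_z = 1.44, requiring 8 patients.

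Neither gives 22. The inputs are insufficient, so this does not show that 22 is wrong.

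**3. What 22 and 25 per group can detect.** 80% power, α = 0.025, one measure, equal standard deviations of change, before whole-brain correction. Noncentral t:
- Within group: λ = d_z√n, n − 1 degrees of freedom.
- Between groups, on post-minus-pre change: λ = d√(n₁n₂/(n₁+n₂)), n₁ + n₂ − 2 degrees of freedom.

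The λ needed for 80% power, divided by the square-root term, gives the detectable effect in standard deviations of change:

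| Contrast, two-sided | λ needed | Divisor | Detectable |
|---|---|---|---|
| Within, 22 | 3.282 | √22 = 4.690 | 0.70 |
| Within, 25 | 3.256 | √25 = 5 | 0.65 |
| Between, 22/22 | 3.179 | √11 = 3.317 | 0.96 |
| Between, 25/25 | 3.166 | √12.5 = 3.536 | 0.90 |

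The Aim 2 power sentence does not state sidedness. One-sided, the between-group figures are 2.868/3.317 = 0.86 and 2.859/3.536 = 0.81.

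**4. Study 2.3.2, if replacements lack the earlier scans.** 40% of 50 is 20 patients retained. No split by group is given. Section 2.1 says botulinum toxin helps much less when VT is present, so an equal split is not assured. Two illustrations, two-sided:

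| Contrast | λ needed | Divisor | Detectable |
|---|---|---|---|
| Between, 10/10 | 3.319 | √5 = 2.236 | 1.48 |
| Within, 10 | 3.601 | √10 = 3.162 | 1.14 |
| Between, 15/5 | 3.319 | √3.75 = 1.936 | 1.71 |
| Within, smaller group of 5 | 4.584 | √5 = 2.236 | 2.05 |

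Under the Human Subjects schedule, with 25 per group fully scanned, the figures are 0.90 between and 0.65 within.

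**The case against.** The strongest reply is that this is a mechanistic imaging proposal. The opening of 2.3 gives Aim 2 two operational tasks: relating symptom improvement to brain change, and studying the combined treatment. Neither is a comparison of SD with SD/VT, and between-group comparisons do reach Aim 2 through PPI and DCM. This limits the point to one component of the hypothesis and to activation. It does not remove it, because 2.1 says the hypothesis will be tested and words it in terms of activation.

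Several stronger readings are tempting, and the documents do not support them:
- *That the before/after comparison is missing.* It is planned in words and powered; it is only absent as a model term.
- *That session by group would test the whole hypothesis.* It tests greater modulation only. The hypothesis also says the greater benefit arises from that modulation, which no such contrast can show. The other half of the central hypothesis, additional abnormalities in SD/VT, already has a group test in 1.3.1.
- *That the group comparison has some particular low power.* Without a standard deviation of change, only detectable differences can be given.
- *That Study 2.3.2 will have 10 per group.* That is one scenario; the Human Subjects schedule implies 25.
- *That retained and replacement patients differ in botulinum toxin response.* Both are described as benefiting from it. The possible difference is in the earlier scans.
- *That a mixed model is required.* With both sessions complete, an ANOVA or a two-sample test on change answers the same question.

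**Conclusion.** The concern holds in this form. The Aim 2 activation model contains neither session nor group, so the greater-modulation component of the central and Aim 2 hypotheses has no stated activation test. The 80% power applies only to before versus after. At 22 per group the between-group difference in change must reach 0.96 standard deviations, against 0.70 for a within-group change; at 25 per group the figures are 0.90 and 0.65. One-sided, the between-group figures fall to 0.86 and 0.81. All assume one measure and equal standard deviations of change, and precede whole-brain correction.

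The statement that Study 2.3.2 has unchanged power does not follow until the documents agree on who has which scans. In the illustrations, the detectable between-group difference rises to between 1.48 and 1.71 standard deviations. Because the gap touches the study's central hypothesis and closing it needs little more than wording, it should be closed before the data are analysed.

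**What to change.** 1. **2.3.1, Data analysis.** Specify session (pre/post), group (SD, SD/VT) and task as fixed and subject as random. Name session within group as the before/after contrast, and session by group as the test of the greater-modulation component only. Name the same contrast for PPI and DCM. For the link to benefit, correlate post-minus-pre imaging change with post-minus-pre symptom change, and do not claim that this shows cause.
2. **2.3.1, Sample size.** State that the 80% power applies only to before versus after. Add the detectable between-group difference with its assumptions and sidedness, or label the SD versus SD/VT comparison as estimation or exploratory.
3. **2.3.2 and Human Subjects Involvement.** Reconcile which patients have which scans. Replace the claim of unchanged power with one based on the number per group contributing to each contrast. If sessions are incomplete, use a model that keeps those patients, and report the within-patient contrast separately because replacements may lack earlier scans.

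**Cost.** Study 2.3.1 needs revised wording and a different group model on the same scans. Study 2.3.2 needs no extra patients or scans if the smaller within-patient number is accepted; keeping 25 per group would require the replacements to have the earlier scans. The drawback is a less favourable power statement for the between-group question.
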